11 STUDY-SPECIFIC INSTRUMENTS

11.1 Cognitive and Clinical Evaluations

11.1.1 Alzheimer's Disease Assessment Scale-Cognitive (ADAS-Cog12)

The ADAS-Cog ([Rosen 1984](#)) is a structured scale that evaluates memory (word recall, word recognition), reasoning (following commands), language (naming, comprehension), orientation, ideational praxis (placing letter in envelope) and constructional praxis (copying geometric designs). Ratings of spoken language, language comprehension, word finding difficulty, and ability to remember test instructions are also obtained. The test is scored in terms of errors, with higher scores reflecting poorer performance and greater impairment. An ADAS-Cog12 version will be used in the current study that includes Delayed Word Recall – a measure of episodic memory ([Mohs 1997](#)). Total ADAS scores can range from 0 (best) to 70 (worse) on the standard 11 items, and then the delayed recall item is added with a score ranging from 0-10, for a maximum score of 80. The ADAS-Cog has been the primary cognitive instrument in previous and ongoing ADCS trials. Psychometrists at each site are required to complete an ADAS-Cog training and certification process prior to administering the evaluation.

11.1.2 Columbia Suicide Severity Rating Scale (C-SSRS)

Consistent with FDA regulatory guidance ([FDA 2012](#)), occurrence of suicide-related thoughts and behaviors will be assessed. The C-SSRS is a scale that captures the occurrence, severity,

and frequency of suicide-related thoughts and behaviors during the corresponding assessment period ([Posner 2011](#)). The scale includes suggested questions to elicit the type of information needed to determine if a suicide-related thought or behavior occurred.

If a suicide-related thought or behavior is identified at any time during the study, a thorough evaluation will be performed by a study physician, and appropriate medical care will be provided.

11.1.3 Logical Memory Test (Wechsler Memory Scale-Revised)

The Logical Memory Test I and II (Delayed Paragraph Recall) is a modification of the episodic memory measure from the Wechsler Memory Scale-Revised (WMS-R) ([Wechsler 1987](#)). In this modified version, free recall of one short story that consists of 25 bits of information will be elicited immediately after it is read aloud to the participant and again after an approximate thirty-minute delay. The total bits of information from the story that are recalled immediately (maximum score = 25) and after the delay interval (maximum score = 25) are recorded. A retention or “savings” score can be computed by dividing the score achieved during delayed recall by the score achieved during immediate recall.

11.1.4 Mini-Mental State Examinations (MMSE)

The MMSE ([Folstein 1975](#)) is a brief, frequently used screening instrument in Alzheimer’s disease drug studies. The MMSE scale evaluates orientation, memory, attention, concentration, naming, repetition, comprehension, and ability to create a sentence and to copy two overlapping pentagons. The MMSE is scored as the number of correctly completed items with a lower score indicative of poorer performance and greater cognitive impairment. The total score ranges from 0 (worse) to 30 (perfect performance).

11.1.5 Neuropsychiatric Inventory (NPI)

The NPI is a well-validated, reliable, multi-item instrument to assess psychopathology in AD based on interview with the study partner ([Cummings 1997](#)). The NPI evaluates both the frequency and severity of 12 neuropsychiatric features, including delusions, hallucinations, agitation/aggression, dysphoria, anxiety, euphoria, apathy, disinhibition irritability/lability, and aberrant motor behavior, as well as sleep and appetite/eating disorders. Frequency ratings range from 1 (occasionally, less than once per week) to 4 (very frequently, once or more per day or continuously). Severity ratings range from 1 (mild) to 3 (severe). The score for each subscale is the product of severity and frequency and the total score is the sum of all subscales.

11.1.6 Clinical Dementia Rating (CDR)

The CDR ([Berg 1998](#)) describes five degrees of impairment in performance on each of six categories of cognitive functioning including memory, orientation, judgment and problem solving, community affairs, home and hobbies, and personal care. The ratings of degree of impairment obtained on each of the six categories of function are synthesized into one global rating of dementia (ranging from 0 to 3), with more refined measure of change available by use of the Sum of Boxes. Reliability and validity has been established, as has high inter-rater reliability. This will be used as a global measure of severity of dementia. Where a full CDR interview is not possible, the abbreviated CDR ([Davis 1991](#)) can be utilized.

11.1.7 Research Satisfaction Survey (RSS)

The Research Satisfaction Survey (RSS) was adapted from the work of Larsen (Larsen 1979) to measures the satisfaction of elderly volunteers in clinical trials to treat or prevent cognitive loss or dementia. The RSS builds on the Client Satisfaction Questionnaire (CSQ-8) which demonstrates a high degree of validity and internal consistency and measured consumer satisfaction with health and human service programs. Higher scores on the CSQ indicate a greater level of satisfaction in service programs¹⁰²; conversely, lower CSQ-8 scores have been associated with higher dropout rates (Lunnen 1998) and missed appointments in treatment settings (Larsen 1983) and in urban Community Mental Health programs (Larsen 1979). Open-ended questions about satisfaction are part of the CSQ, and allow participants to provide feedback about specific operational procedures of a particular service program (Larsen 1979). The RSS is similarly designed with a 7- item survey and may include additional items to inquire about the specific aspects of a given trial. Four items are designed to be answered with a modified Likert scale and can be used to create a summary score with a range of 4-16, which can be analyzed with parametric statistics; three items provide for open ended responses about the intervention, the assessments and the frequency of visits and may be used to understand retention rates.

12 STUDY-SPECIFIC PROCEDURES

12.1 Safety Assessments

Safety will be evaluated by monitoring for changes in the parameters summarized below, including any AEs/SAEs as reported by subjects or observed by the clinical staff, or by the use of concomitant medication during the study.

12.1.1 Physical and Neurological Examination

A medically qualified professional will perform a brief physical examination that consists of a review of the major body systems (i.e., skin, head/ears/eyes/nose/throat (HEENT), cardiovascular, pulmonary, abdomen, musculoskeletal, and extremities) and a brief neurological examination which will include an assessment of cranial nerves, strength, coordination, reflexes, sensation, tremor, gait and mental status. Assessments of height, weight, and vital signs (systolic and diastolic blood pressure, pulse, temperature, and respiration) are included.

12.1.2 Electrocardiogram (ECG)

An appropriately qualified individual will conduct a standard 12-lead resting ECG. The ECG report must be reviewed, signed, and dated by the site PI (or a medically-qualified individual delegated by the site PI). Those with clinically significant ECG findings will be referred for follow-up as deemed appropriate by the investigator and may be excluded from the study.

12.1.3 Clinical Laboratory Evaluations

Blood and urine samples will be obtained for clinical safety lab assessments as described in the Schedule of Events (Appendix 1). The following table lists the clinical safety lab tests that will be assessed by the central lab at three time points: the screening visit, the pre-confinement visit, and the end of the 36-hour sampling period.

Table 4. Clinical Safety Lab Tests

CLINICAL SAFETY LAB TESTS		
METABOLIC PANEL	COMPLETE BLOOD COUNT	URINALYSIS
Sodium (Na)	White Blood Cell Count (WBC)	Color
Potassium (K)	Red Blood Cell Count (RBC)	Appearance
Chloride (Cl)	Hemoglobin (Hb)	Specific Gravity
Carbon Dioxide (CO ₂)	Hematocrit (HCT)	pH
Blood Urea Nitrogen (BUN)	Mean Corpuscular Volume (MCV)	Blood
Glucose	Mean Corpuscular Hemoglobin (MCH)	Glucose
Calcium (Ca)	Mean Corpuscular Hemoglobin Concentration (MCHC)	Protein
Creatinine (Crn)	Red Blood Cell Distribution Width (RDW)	Ketones
Bilirubin Total	Mean Platelet Volume (MPV)	Leukocyte Esterase
Albumin	Platelet Count (PLT)	Nitrite
Protein (NOS) Total		Urobilinogen
Glutamic-Oxaloacetic Transferase (AST, SGOT)		Bilirubin
Glutamic-Pyruvate Transferase (ALT, SGPT)		Pregnancy Test (only screening visit)
Alkaline Phosphatase NOS		
COAGULATION PANEL		
	PPT/PTT	
	[Screening Visit ONLY]	

Routine laboratory samples (including CSF) that are collected at the admission before the LP, the post-confinement visit, and the 12-hour observation (if necessary) should be analyzed by a CLIA/CAP (or equivalent) certified local laboratory. Lab reports will be reviewed, signed and dated by the site PI (or a medically qualified individual delegated by the PI). If a value is outside of the laboratory's normal range, the clinician will indicate if the value has clinical significance. Those results that are deemed clinically significant may need to be repeated and may require follow up with the subject's primary care physician for further evaluation.

12.2 Biofluids

12.2.1 CSF for Biomarkers

Standard Lumbar Puncture:

A lumbar puncture will be performed as part of the screening visit, in the morning (before 10am is recommended), after an overnight fast. 2ml CSF will be sent for analysis by the site (total protein, glucose, cell count) to a local lab. The remaining CSF will be placed into a 14 ml conical polypropylene tube, inverted gently 3-4 times, then centrifuged at 1500 x g for 10 minutes at room temperature. The supernatant should be aliquoted into 2.0 ml tubes, frozen at -80°, and shipped overnight to the ADCS Biomarker Core. The ADCS Biomarker Core will subsequently send these samples to C2N for processing and analysis according to Biomarker core SOPs. Analyses will include AD biomarkers (e.g., A β , sAPPs, tau).

CSF samples will be banked in the biospecimen repository of the ADCS Biomarker Core for various future research studies; access to samples will be granted according to SOPs established by ADCS Biomarker Core.

Prior to the LP, a coagulation panel will be obtained to rule out a clotting disorder. Participants taking an anti-platelet agent (e.g., Plavix) must be discontinued from that agent for a minimum of 5 days prior to the lumbar puncture. These participants may continue with the agent after a minimum of 24 hours post LP. Participants who are taking anticoagulants (e.g., warfarin (Coumadin) and/or dabigatran (Pradaxa) may not undergo an LP and are not suitable to participate in this study.

When done at the same visit, the LP should occur after the MRI scan. When done at the same visit, if the MRI scan can only be scheduled prior to the LP, the site must contact ADCS Clinical Operations for permission before proceeding. In the unplanned event that the MRI does not precede the LP, there should be a minimum window of 72 hours between the MRI and the LP. LP under fluoroscopy is permitted; however, the site must contact ADCS Clinical Operations for permission before proceeding. Site personnel should advise the subject that use of fluoroscopy (x-rays) involves exposure to radiation.

Each study participant or a person designated to speak for them will be contacted by phone approximately 24 hours after the LP to confirm participant well-being and any adverse events.

CSF Sampling:

A total volume of 116 mL of CSF should be collected during the CSF catheter sampling during the confinement visit. At hours 0, 2, 4, 6, 8, 10, 12, 14, 16, 18, 20, 22, 24, 26, 28, 30, 32, 34, and 36, 6 mL of CSF is collected.

NOTE: If unable to obtain a total of 6 mL CSF at any given collection time (e.g., due to participant headache or participant's CSF production level) the maximum amount will be obtained and ADCS Clinical Operations must be notified.

To clear blood associated with needle insertion, the first 1-2 mL (or more if needed) of CSF should will be discarded. In addition, at 0 hours, 1-2 ml CSF (or volume per Local laboratory requirements) will be sent ambient to the local laboratory for protein, glucose, and cell counts. At the 36 hours, an extra 2ML of CSF should be sent to the local lab for protein, glucose, and cell counts. The remaining CSF should be placed into a 14 ml conical polypropylene tube, inverted gently 3-4 times, and then centrifuged at 1500 x g for 10 minutes at room temperature. Then the supernatant should be aliquoted into 2.0 ml tubes and frozen at -80° and shipped overnight to the ADCS Biomarker Core.

Each study participant or a person designated to speak for them will be contacted by phone one day after being discharged from the confinement visit. The participant will be asked about their well being and the occurrence of any adverse events.

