7.9 Concomitant Medications

7.9.1 Prohibited Concomitant Medications

Current use of anti-coagulants (e.g., warfarin (Coumadin), dabigatran (Pradaxa) or anti-platelet drugs (e.g., aspirin, Plavix)), other than aspirin up to a dose of 325 mg per day, is prohibited. Prospective subjects who can safely discontinue these medications for 4 weeks before screening and remain off these medications throughout the study, can be considered for inclusion in the study.

Use of the following medications is prohibited within 4 weeks of screening and throughout the study except as noted in Section 7.9.2:

- specific psychoactive medications (tricyclic antidepressants, antipsychotics (except ≤ 50 mg quetiapine daily, risperidone ≤ 1.5 mg/day, olanzapine ≤ 5 mg/day, and aripiprazole ≤ 10 mg/day)
- mood-stabilizing psychotropic agents (e.g., lithium salts)
- psychostimulants
- opiate analgesics
- antiparkinsonian medications

- anticonvulsant medications
- systemic corticosteroids
- CNS active antihistamines for allergy or sleep (daily use)

Investigational agents are prohibited 4 weeks prior to entry and for the duration of the trial. Also, exclusionary, is previous treatment with an investigational small molecule with anti-amyloid properties or passive immunization against A β within 1 year of entry or previous treatment with an active immunization against amyloid. This will also include AduhelmTM, an A β -directed monoclonal antibody that received accelerated FDA approval for treatment of early AD but which is prohibited in this study.

Initiation of prohibited medications during the course of the study is discouraged, however, if an excluded medication is initiated after screening, the site should consult with the Project Directors and Medical Monitor for further guidance.

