9.5.2 Confinement Visit

The confinement visit will last just over 2 days and will consist of four phases: admission, 36-hour sampling, 12-hour observation, and discharge. Subjects will be provided with meals (note: some restrictions are specified below) and sleeping accommodations during this visit. For a complete list of all visit procedures, refer to the Schedule of Events (Appendix 1) and to the Confinement Visit Diagram (Appendix 3).

Phase 1: Admission

Subjects should arrive fasted in the early morning after an overnight fast. Clinical safety labs will be drawn and sent to the local lab for analysis.

Study drug compliance over the preceding days will be assessed. If there is an insufficient level of drug compliance (less than 80% overall and or less than 80% in the last week), the site must consult with the Project Directors and Medical Monitor regarding timing and conduct of the remaining confinement visit procedures. It is possible that subjects will be discontinued early from the study due to insufficient study drug compliance.

Admission visit procedures include conducting a brief Physical and Neurological Exam, collecting vital signs, reviewing and recording adverse events and concurrent medications. Please refer to Appendix 3.1, Confinement Visit Phase 1: Admission Diagram.

Phase 2: 36-Hour Sampling

For an overview of the 36-Hour Sampling time points, please refer to the Confinement Visit Schedule of Events (Appendix 3.2b).

If no medical or compliance concerns are identified during the admission procedures, the subject will move on to the 36-Hour Sampling Phase, which entails the following procedures:

1. Place an intravenous line (for infusion) as well as a second venous line for blood sampling
2. Place the CSF catheter
3. Collect initial samples of blood and CSF

4. Administer assigned study drug (will vary based on blinded treatment assignments) at 0 hours
5. Begin the $^{13}\text{C}_6$ -labeled “heavy” leucine infusion. Subjects will receive an initial bolus of 3 mg/kg over 10 minutes, followed by 8 hours and 50 minutes of continuous intravenous infusion at a rate of 2 mg/kg/hour. The total leucine administration with the bolus is 9 hours
6. Provide a low leucine meal (NOTE: all food provided during the heavy leucine infusion must conform to low leucine dietary guidelines; refer to Appendix 4, Sample Low Leucine Menu and to the Procedures Manual for more details)
7. Continue with the following for 36 hours:

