10.1 Reasons for Early Discontinuation

Participants may withdraw from the study at any time as stated in the informed consent document given to the participant at the screening visit. Participants may also be discontinued from treatment/study for reasons such as the following:

- Adverse experience: The participant has experienced an adverse event that, in the opinion of the investigator, requires early termination. This may include abnormal laboratory values.

- Death.
- Safety risk: Any participant who becomes a safety risk to themselves during the trial will be withdrawn.
- Protocol violation: The participant fails to meet protocol entry criteria or does not adhere to protocol requirements.
- Non-compliance: The participant is non-compliant with completion of study-related evaluations and/ or intake of study drugs.
- In the investigator's judgment, it is in the participant's best interest to discontinue participation in the study.
- Development of suicidal or homicidal ideation requiring hospitalization or confinement.
- Participant has need for a medication prohibited by the protocol.
- Consent is withdrawn. The participant wishes to withdraw from the study, or the legally authorized representative wishes that the participant be withdrawn.
- The study is terminated by the Sponsor/Coordinating Center, alone or at the recommendation of the Data Safety Monitoring Board.
- Lost to follow up. Participant could not be recalled back to conduct follow up visits.
- Loss of informed study partner. The participant no longer has a responsible study partner to oversee participant visits and administration of study drug.
- Coordinating Center (ADCS) request. The Coordinating Center determines it is in the participant's best interest to discontinue participation from the treatment and or study.

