APPENDIX 2: STUDY SCHEMATIC DIAGRAM

APPENDIX 3: CONFINEMENT VISIT DIAGRAM**Appendix 3.1 Confinement Visit Phase 1: Admission Diagram**

Conditions	Check
Arriving early pre-lunch	
Overnight fasting	
Study Drug Compliance	
Physical exam	
Neurological exam	
Clinical safety labs	
Vital signs	
AEs reviewed and recorded	
Con Meds reviewed and recorded	

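### Protocol 12.2.1 allows Plavix with a 5-day stop and resumption 24 hours after the screening lumbar puncture, although 7.9.1 bars it from 4 weeks before screening to the end of the study

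*Protocol*

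**What the plan says.** Two sections of the protocol give rules for anti-platelet drugs, and both use Plavix as an example.

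- **Section 7.9.1 (Prohibited Concomitant Medications).** Current use of "anti-platelet drugs (e.g., aspirin, Plavix)), other than aspirin up to a dose of 325 mg per day, is prohibited". The route in for other users is narrow. It is open to "Prospective subjects who can safely discontinue these medications for 4 weeks before screening and remain off these medications throughout the study".
- **Section 12.2.1 (CSF for Biomarkers), under the Standard Lumbar Puncture subheading.** "Participants taking an anti-platelet agent (e.g., Plavix) must be discontinued from that agent for a minimum of 5 days prior to the lumbar puncture". The next sentence reads: "These participants may continue with the agent after a minimum of 24 hours post LP". The sentence after that treats anticoagulants differently: people taking those may not have an LP and are unsuitable for the study.

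The inclusion and exclusion lists in 8.1 and 8.2 contain no anti-platelet criterion. The protocol does not say which section governs where the two differ.

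**The concern.** Section 12.2.1 is where site staff would look when preparing a participant for the LP. Read alone, it describes Plavix users as participants whose drug is paused and then continued. Its contrast with anticoagulant users, who are declared unsuitable, strengthens that impression. Section 7.9.1 puts both classes under the same prohibition and the same 4-week condition.

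The stake is procedural safety. The screening LP is followed some weeks later by an indwelling lumbar catheter with 36 hours of CSF sampling. Section 5.3 lists epidural or subdural bleeding, paralysis and nerve-root injury among the potential risks of these procedures. An instruction that lets a prohibited anti-platelet drug be resumed between the two procedures should not stand beside one that forbids it.

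**Working it through.** There is no stated statistical figure to reproduce. The check is a comparison of the two rules, with simple date arithmetic.

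**Inputs**

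- Time off Plavix under 7.9.1: 4 weeks before screening, then throughout the study.
- Time off under 12.2.1: at least 5 days before the LP, with resumption allowed from 24 hours after it.
- The LP is part of the screening visit (9.2), so it falls on or after the start of screening.
- Confinement admission is 21-23 days, ± 2 days, after the first dose (9.5).

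**Time off before the screening LP**

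- 7.9.1: 4 × 7 = 28 days before screening, hence at least 28 days before the LP.
- 12.2.1: at least 5 days.
- Difference between the two minimum requirements: at least 28 − 5 = 23 days.

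This leaves out the exception in 9.2.1, under which an LP done for another study within 90 days before baseline may be used. Such an LP can precede screening, so the 28-day count does not carry over to it.

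**Use after the screening LP**

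| | 7.9.1 | 12.2.1 |
|---|---|---|
| Resumption of Plavix during the study | Not allowed | Allowed from 24 hours after the LP |

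**Does the permitted resumption fall before the catheter?** Yes. The earliest admission is 21 − 2 = 19 days after the first dose, and study drug is dispensed only at baseline, once screening is complete. Resumption one day after the screening LP therefore becomes available well before catheter placement.

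**Does it matter which LP the 5-day hold refers to?** The subheading and opening sentence point to the screening LP. The Synopsis, 9.5.2 and 12.1.3 also use LP wording for the confinement procedure, so a site might apply the hold there too. Such a participant would still have been taking Plavix during the study, contrary to 7.9.1. The conflict stands on either reading.

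**The case against.** The strongest reply is that 12.2.1 is a specimen-handling section and 7.9.1 is the section that decides which drugs are allowed. A 28-day washout satisfies a 5-day minimum, and a statement that someone may continue a drug obliges nobody to do so. A site that obeys 7.9.1 therefore breaches nothing in 12.2.1. That is correct, and it means the two rules are not logically impossible to satisfy together. What remains is a permission in one section for something another section forbids, with nothing stated to cancel it.

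The protocol also has safeguards. Under 7.9.1, "if an excluded medication is initiated after screening, the site should consult with the Project Directors and Medical Monitor for further guidance". Section 10.1 lists as a possible reason for discontinuation: "Participant has need for a medication prohibited by the protocol". Medications are reviewed at baseline, at the Day 14 call, at pre-confinement and at admission. Section 9.5.2 adds a gate: "If no medical or compliance concerns are identified during the admission procedures, the subject will move on to the 36-Hour Sampling Phase". These lower the practical risk but do not remove the conflict. The consultation rule is worded for a drug started after screening, and a site that reads 12.2.1 as permission may see continued Plavix as already allowed. The Appendix 3.1 admission checklist says only "Con Meds reviewed and recorded"; it does not ask whether a barred agent is in use.

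A reader might go further and infer that the protocol wrongly omits an aspirin hold before the confinement catheter. The documents do not support that. Section 7.9.1 deliberately permits aspirin up to 325 mg per day, and section 5.3 does not tie the bleeding risk to it. Nothing in either document shows that a hold at that dose is needed. The LP wording used for the catheter could carry the 5-day hold across. The content of Appendix 3.2 is not readable in the available text and the procedures manual is not among the documents, so either may cover the matter.

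A reader might also turn the visit windows into a range of days on Plavix before the catheter. That would describe hypothetical exposure under one reading of the text and would not measure risk.

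**Conclusion.** The inconsistency is real and confined to Plavix and the other anti-platelet agents that 7.9.1 prohibits. Section 12.2.1 accepts at least 5 days off before the screening LP where 7.9.1 requires at least 28, and it allows resumption where 7.9.1 allows none.

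The documents do not support the stronger conclusion that the protocol as a whole lets Plavix users reach the catheter. That would happen only if a site relied on 12.2.1 over 7.9.1 and the later medication reviews did not catch it. If 7.9.1 is followed, there is no such exposure. The documents give no count of Plavix users among candidates, so the number affected may be zero of up to 24.

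The comparison assumes that the LP is done within the trial's own screening period and that no case-by-case exception has been agreed with the Project Directors and Medical Monitor. The point is one of safety consistency. It should be corrected because the text is wrong against 7.9.1 and the correction is cheap. It has no bearing on any endpoint, power figure or SAP analysis.

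**What to change.** Amend the two hold-and-resume sentences in 12.2.1:

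- Remove Plavix as the example, and exclude every anti-platelet agent that 7.9.1 prohibits.
- State that those agents are barred under 7.9.1 from 4 weeks before screening until the end of the study.
- Leave the existing pre-LP hold in place for the permitted agent, aspirin up to 325 mg per day. Deleting the sentences outright would remove that as well.

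The cost is a short wording amendment. Under 18.2 it needs prior Coordinating Center approval and IRB approval before use. Sample size, randomization, endpoints and analyses stay as they are.
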